### **PCI Group**

*The PCI group will be followed by their cardiologist and will receive usual clinical care. Subjects in both groups will be Veterans who receive their routine care at our facility, so it will be easier to gather pertinent information and to ascertain that subjects in both groups are receiving optimal medical therapy (including blood panels and blood pressure every 4 months). The testing schedule, timelines, and all procedures (except exercise training and PCI) will be similar between the PCI and exercise groups. Physical activity patterns will be monitored in a similar fashion in both the PCI and exercise groups. At each 4 month visit, the Co-PI ([name]) will review the overall adequacy of care for each subject in the study.*

### **Subject Burden**

*We anticipate that baseline evaluations for each subject will require a total of 2 to 3 hours, with the exercise test and PET/CT evaluations performed on separate days. This will include questionnaires, health history, exercise test and PET/CT evaluations, and blood panel. For the exercise group, the total number of visits to the hospital will be approximately 38 (including exercise training sessions), and for the PCI group the total number of visits will be approximately 8.*

### **Cost Effectiveness Analysis**

The cost analysis will examine two research questions in this study:

1. Does exercise training reduce healthcare costs as compared to standard PCI after 1-year?; and
2. Is a program of exercise rehabilitation more cost-effective compared to PCI?

These findings are considered preliminary for a larger study, given the study's sample size. *In order to derive all the necessary information related to the cost analyses, only subjects who receive their routine care at the VA Palo Alto HCS will be recruited for the study (approximately 97% of patients referred for PCI receive their care at our facility).*

For the purpose of this cost analysis, "effectiveness" of the intervention will be defined by the primary outcome at the patient level. That is, changes from baseline in individual global myocardial perfusion reserve with dipyridamole at 1-year will be used to calculate the effect. Individual level change scores will be associated with individual intervention net-costs (intervention delivery minus healthcare expense cost-savings), to provide confidence intervals of each economic value.

**Estimating Intervention's Costs and Healthcare Expenses.** The cost identification analysis will be from the provider's (VA's) perspective because of the life-long entitlement of VA services for veterans. We will identify the VA expense to produce the service in each intervention or study arm. Furthermore, since we hypothesize a net cost-savings to the VA in the long-run, we must collect the VA healthcare utilization during the study period and estimate the total expense. This valuation step is complicated by the current state of cost accounting in the VA. Both the internal VA Decision Support System (DSS) valuation and an external reference created from national Medicare reimbursement values will be used (91,92). We have previously used the VA DSS to

evaluate health care costs associated with fitness (25) and physical activity patterns (93). This approach is consistent with the VA HSR&D Services' Health Economics Resource Center's (HERC) 2002 recommendations, as long as everything is within one facility.

***Intervention's Delivery Expense.*** We will first estimate the cost of delivering care for the intervention and for routine care (PCI). The incremental cost of production for the intervention is expected to be the additional personnel time required to add the incremental intensity of care. We will follow the framework proposed by Donaldson (94) where personnel, materials, supplies and space are included in this estimate. To the extent possible, DSS data will be used, which is a micro-costing approach. Such cost-identification must be at the patient-level with comparison of means at the group level in order to gain confidence intervals of the estimates.

***Intervention Cost Identification Data Collection.*** The provider's perspective constrains cost identification to the local facility's personnel time, materials, procedures, etc. The VA computerized medical records system (CPRS) template of patient encounter times, personnel and procedures, and medications involved will be quantified. This will document the appropriate expenses. Base salary and fringe for all personnel involved with the patient will be determined from personnel files. Space required for each encounter will be identified and valued by VA estimates.

***Healthcare Utilization and Expense Estimates.*** The delivery costs must then be offset by the healthcare cost-savings (as compared to the non-intervened group) based in VA healthcare utilization for each patient to acquire the *net cost-savings*. The difference between the means of each group, after ranking in effectiveness order, provides the incremental cost of the cost-effectiveness analysis. Issues of discounting dollar amounts for inflation and time value of money will be handled by sensitivity analysis and methods consistent with Gold et al. (95). Concerns for patient preferences and a societal estimation are not of concern in this study.

***VA Utilization Extractions and Cost-Savings Estimates.*** Using the VA system (CPRS), we will track the actual patient care utilization (e.g., inpatient and outpatient visits, events, hospitalizations, procedures and prescriptions) during the study period for each patient in the trial. This will permit the comparison of the expected differences in hospitalizations, physician visits, medications and ER visits. The difference in units of service (physician / primary care visits; ER visits and hospitalizations) will be valued using the Medicare national average, without differentials for teaching affiliation and geographic location, and by national average DSS values from the VA. Medical events are chronologically ordered for each patient, and reassembled into one-year episodes of care for both pre- and post intervention periods to acquire the cost-savings impact of the intervention at the patient-level. Thus, a patient's individual cost-savings as well as a comparison against the routine care group's mean will be obtained.

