### ***Statistical Analysis Plan***

***Key Question #1:*** Does exercise training favorably alter coronary anatomy and function as determined by non-invasive imaging techniques?

***Statistical Analysis, Key Question #1.*** Myocardial blood flow using PET at rest and following dipyridamole infusion will be expressed as ml flow/100 g/min. The primary outcome, myocardial perfusion reserve, will be calculated as the ratio of the myocardial blood flow during stress (e.g. after dipyridamole) and the myocardial blood flow at rest. Differences within and between groups will be assessed using repeated measures ANOVA, with group (exercise vs. PCI) and test (baseline vs. 1-year) as factors. Post-hoc procedures will be performed using the Bonferonni method.

***Key Question #2:*** Can a program of exercise therapy improve outcomes (exercise capacity, symptoms, repeat hospitalizations, and quality of life) in patients with CAD that are equivalent or superior to PCI?

Statistical Analysis, Key Question #2. These secondary outcomes will include changes in peak  $VO_2$  and other cardiopulmonary exercise test responses (including  $VO_2$  at the ventilatory threshold, exercise time, and heart rate recovery), quality of life measures, and lipid panels. Paired tests will be used (paired t-test or Wilcoxon signed rank test) to compare continuous variables between groups at baseline. Differences between groups after the 1-year study period will be assessed by repeated measures ANOVA, with group (exercise vs. PCI) and test (baseline vs. 1-year) as factors. Post-hoc procedures will be performed using the Bonferroni method.

**Key Question #3:** Will exercise training reduce costs as compared to standard PCI after 1-year?

Statistical Analysis, Key Question #3. Comparison of costs will be made for the individual level change scores using the intervention net-costs (intervention delivery minus healthcare expense cost-savings). Cost effectiveness of the intervention will be defined by the primary outcome at the patient level. That is, changes from baseline in individual global myocardial perfusion reserve using PET at 1-year will be used to calculate the effect. Differences in costs between groups will be assessed using ANOVA.

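### The 1-year net cost subtracts savings priced at national averages from delivery costs whose staff component is priced at the facility's own pay, so the between-arm difference depends on the local-to-national price ratio

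*Combined protocol and SAP*

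**What the plan says.** All references are to the combined protocol and SAP.

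- **Outcome.** The Statistical Analysis Plan, Key Question #3, states: "Comparison of costs will be made for the individual level change scores using the intervention net-costs (intervention delivery minus healthcare expense cost-savings". The arms are then compared by ANOVA.
- **Delivery term.** In the Cost Effectiveness Analysis, the paragraph on collecting intervention cost data sets the scope: "The provider's perspective constrains cost identification to the local facility's personnel time, materials, procedures, etc". For staff it says: "Base salary and fringe for all personnel involved with the patient will be determined from personnel files". For space: "Space required for each encounter will be identified and valued by VA estimates". The paragraph on delivery expense adds: "To the extent possible, DSS data will be used, which is a micro-costing approach". It covers both arms, with PCI as the routine-care arm, and expects the extra cost of the intervention to be mainly staff time.
- **Savings term.** The paragraph on VA utilization has the difference in clinic visits, emergency visits and hospital stays "valued using the Medicare national average, without differentials for teaching affiliation and geographic location, and by national average DSS values". Procedures and prescriptions are also tracked, but no price source is named for them.
- **Sensitivity analysis.** The only one named for costs concerns inflation and discounting.

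**The concern.** One subtraction uses two price levels. By stripping geographic and teaching differentials, the plan accepts that prices vary with place and type of hospital, but it removes that variation only from the savings. The staff part of delivery keeps the facility's own pay. Valuing savings by both Medicare and DSS does not help, because both values are national.

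The mismatch does not cancel between arms unless the locally priced delivery cost is the same in both. That is unlikely when one arm receives a procedure and the other a year of staff-run sessions. The resulting difference is neither the facility's cost nor a national VA cost. Confidence intervals built from patient-level variation would not show the shift, because the price ratio is the same for every patient. The same figure supplies the incremental cost in the cost-effectiveness analysis, which is meant to inform a larger study.

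**Working it through.** The plan gives no unit prices, no price ratio and no expected net cost, so there is no stated figure to reproduce. The check is algebraic, followed by illustrations with assumed amounts.

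**Inputs**
- r = local price divided by national price. Not in the documents; assumed range 0.8 to 1.5.
- dL = locally priced part of the delivery-cost difference (exercise minus PCI), in national-price dollars. Staff pay belongs here.
- dN = the rest of the delivery-cost difference, taken as nationally priced.
- dS = utilization saving at national prices.

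**Formulas for the exercise-minus-PCI net cost**
- As planned: r·dL + dN − dS
- All national: dL + dN − dS
- All local, with one ratio for everything: r·(dL + dN − dS)
- Shift from the all-national figure: (r·dL + dN − dS) − (dL + dN − dS) = **(r − 1)·dL**

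For each $1,000 of dL the shift is −$200 at r = 0.8, +$200 at r = 1.2 and +$500 at r = 1.5. If dL is negative, the signs reverse. On either single basis the sign of the result does not depend on r. Under the mix it can: with dN = 0 and both dL and dS positive, it changes at r = dS/dL.

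**Illustration 1: where the index PCI is counted.** Assumed round amounts at national prices: exercise delivery $5,000, PCI $10,000, further saving $1,000, with all delivery locally priced. The all-national result is 5,000 − 10,000 − 1,000 = −$6,000.

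| r | PCI as local delivery: r(5,000 − 10,000) − 1,000 | PCI as national hospital stay: 5,000r − 10,000 − 1,000 |
|---|---|---|
| 0.8 | −$5,000 | −$7,000 |
| 1.0 | −$6,000 | −$6,000 |
| 1.2 | −$7,000 | −$5,000 |
| 1.5 | −$8,500 | −$3,500 |

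The same ratio moves the result in opposite directions. If only half of each delivery cost is locally priced, the shift halves: at r = 1.2 the two results become −$6,500 and −$5,500.

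**Illustration 2: a sign change is possible.** Assumed dL = $2,000, dN = 0, dS = $2,400. The planned result is 2,000r − 2,400: −$400 at r = 1.0, $0 at r = 1.2, +$200 at r = 1.3 and +$600 at r = 1.5. This requires exercise to cost more than PCI within the delivery term.

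**The case against.** The strongest reply is that only staff pay is clearly local. Restricting cost identification to the local facility may say which resources are counted, not how they are priced. Space is valued by VA estimates that are not described as local, materials have no named price source, and the DSS data used for delivery are not labelled local or national. If they are national, much of the mismatch disappears. This stands. A reader might infer that the whole delivery term, space included, is locally priced, and the documents do not support that. The mismatch remains for staff pay, which the plan expects to be the main extra cost of the intervention.

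A reader might also see a contradiction with the statement that the costing approach follows the cited recommendations "as long as everything is within one facility". The text does not bear this out. The same paragraph includes a national Medicare reference in the approach being qualified, and the condition may concern only where patients receive care. Recruitment is limited to patients whose routine care is at this facility.

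A third inference is a size. Take the roughly $10,000 reported in the Background as PCI's delivery cost, assume $2,000 to $4,000 for exercise and r = 1.4. The shift is then 0.4 × (−8,000) to 0.4 × (−6,000), or −$3,200 to −$2,400, up to about a third of that $10,000. The $10,000, however, is PCI's added cost over optimal medical therapy in another trial, not its delivery cost here, and the other inputs are assumed. Even with these inputs exercise stays cheaper: with PCI counted as a national hospital stay, 1.4 × 4,000 − 10,000 = −$4,400 before any further saving.

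Finally, cost is a secondary objective and the plan calls these findings preliminary because of the sample size. That limits the importance of the point but does not answer it.

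**Conclusion.** The concern holds in limited form. As written, net cost combines staff time at the facility's pay with utilization at national averages, and no step or sensitivity analysis reconciles them. The between-arm result is shifted by (r − 1) times the locally priced part of the delivery-cost difference, or $200 per $1,000 at an assumed r = 1.2.

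The documents determine neither the total nor the direction. Both depend on r, on how much of delivery is locally priced, and on whether the index PCI is counted as delivery or as a nationally priced hospital stay. A reader might conclude that the plan is biased in favour of exercise, or that its cost conclusion would be wrong. Neither follows: Illustration 1 shows shifts both ways without a change of sign, and the reversal in Illustration 2 needs a particular assumed scenario. The primary endpoint and sample size are unaffected. This should be corrected before costs are analysed.

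**What to change.** State in the Cost Effectiveness Analysis that, within each analysis, delivery and utilization are valued on one price basis.

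- **One basis, for example as the main analysis:** measured staff time at national VA salary rates, with national DSS or Medicare values for utilization. Space, materials and any DSS-derived delivery costs go on the same national basis.
- **The other basis, as sensitivity analysis:** everything at facility DSS costs and local salaries. The provider perspective would also allow this as the main analysis; what matters is to choose one in advance.
- **Index PCI:** say whether it belongs to delivery or utilization, and count it once.
- **Price sources:** name them for space, materials, procedures and prescriptions, and say whether each is local or national.

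The resource quantities collected do not change. The cost is one extra set of unit prices and some wording. The downside is that one of the two bases, whether the facility's budget view or the national view, is no longer the main figure.

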## RESEARCH DESIGN and METHODS

## Study Population

*Stable patients between the ages of 50 and 70 years who have lesions appropriate for PCI based on American Heart Association/American College of Cardiology criteria will be considered for the study. Only patients with a good prognosis (annual mortality <1% based on VA multivariate scores (56, 57) will be considered. Patients with left main disease or proximal LAD disease will be excluded. Additional exclusion criteria include those with unstable angina, a history of heart failure (EF ≤30%), pacemakers, atrial fibrillation, myocardial infarction within the last 3 months, diabetes, and those with orthopedic problems interfering with the ability to exercise regularly.*

**Recruitment.** *A study flow chart including screening, baseline evaluations, and procedures is presented in Appendix I. Subjects will be recruited from the following populations: 1) patients referred for a clinically-indicated stress myocardial perfusion study (nuclear, echo, or CT); and 2) patients who have a positive exercise test with >1.0 mm ST-segment deviation from baseline on a standard treadmill exercise test, estimated to have a >80% probability of disease based on VA scores (56,57). There are approximately 2,500 patients who undergo these evaluations for CAD at our facility annually, providing a large pool of potential subjects for the study. Potential subjects will be referred for PET/CTA, and baseline PET/CTA findings will confirm patients meet inclusion and exclusion criteria. If the PET/CTA studies show significant ischemia in a moderate to large territory supplied by a significantly diseased vessel, these patients will be recruited for the study.*

*PET is considered the gold standard for stress perfusion imaging. Thus, only patients who have moderate to large areas of moderate to severe perfusion defects will be recruited. In addition, only subjects who have a perfusion defect on PET supplied by a significantly diseased artery on CTA will be recruited. Only subjects actually referred for PCI will be considered for the study. A partial waiver of authorization (per HIPAA) will be obtained in order to access medical records or contact individuals for the purpose of study recruitment. A total of 64 subjects will be recruited; randomization will be stratified by age, exercise capacity, and BMI so that these variables will be matched evenly between exercise intervention and PCI groups.*

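### The pre/post cost saving is not an intervention effect, and the plan sets no index date and no rule for counting the PCI once

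*Combined protocol and SAP*

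**What the plan says.** The cost question is a comparison between arms: "Does exercise training reduce healthcare costs as compared to standard PCI after 1-year" (Cost Effectiveness Analysis, first research question). The plan describes the saving that feeds it in three places.

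- *VA Utilization Extractions and Cost-Savings Estimates*: each patient's events are "reassembled into one-year episodes of care for both pre- and post intervention periods to acquire the cost-savings impact of the intervention at the patient-level". The same paragraph adds: "Thus, a patient's individual cost-savings as well as a comparison against the routine care group's mean will be obtained".
- *Healthcare Utilization and Expense Estimates*: "The delivery costs must then be offset by the healthcare cost-savings (as compared to the non-intervened group"). It continues: "The difference between the means of each group, after ranking in effectiveness order, provides the incremental cost of the cost-effectiveness analysis".
- *Statistical Analysis Plan, Key Question #3*: "Comparison of costs will be made for the individual level change scores using the intervention net-costs (intervention delivery minus healthcare expense cost-savings"), and then "Differences in costs between groups will be assessed using ANOVA". No adjustment for earlier cost is mentioned.

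Patients reach the trial as "patients referred for a clinically-indicated stress myocardial perfusion study (nuclear, echo, or CT") or through a positive exercise test. PET/CTA and a referral for PCI follow (Study Population, Recruitment). Randomisation comes after consent and the baseline exercise test (Screening Process and Informed Consent).

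No section gives the date that separates the pre-year from the post-year. Imaging and fitness follow-up, by contrast, is timed from randomisation (Statement of the Problem). The delivery expense covers PCI as well as exercise (Intervention's Delivery Expense), and the utilisation extract also includes procedures and hospitalisations.

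**The concern.** Three things looked wrong.

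First, the plan describes a before/after difference within one patient as the impact of the intervention. The earlier year contains the stress test, imaging and visits that led to enrolment. That spending falls away afterwards whatever the treatment.

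Second, the split is labelled by the intervention and has no date. Exercise starts once baseline testing is complete (Timeline) and lasts a year, whereas PCI is a single procedure with no stated timing. If the split is tied to the intervention, the windows could differ by arm. The PCI, probably the largest single cost item in its arm, could then fall in the pre-year, in the post-year, in delivery cost, or in two of these.

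Third, the saving is defined once against the other group and once against the patient's own earlier year. Nothing says which one enters the net cost.

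At stake is Secondary Objective #2, the one-year cost difference, estimated from 25 to 32 patients per arm.

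**Working it through.** **1. The plan's own figures.** There is no sample size, SD or correlation for cost. The stated numbers concern perfusion reserve, and they reproduce. SD of change = sqrt(0.20² + 0.20² − 2 × 0.65 × 0.20 × 0.20) = 0.167. n per group = 2 × (1.96 + 0.84)² × (0.167/0.135)² ≈ 24.02, rounded up to 25. Enrolment = 25/0.8 = 31.25, rounded up to 32. The 0.65 belongs to perfusion reserve and cannot be used for cost.

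**2. Work-up in the pre-year.** With the pre/post saving, net cost = delivery − (pre − post) = delivery + post − pre. Add a work-up cost W to every patient's pre-year. Each patient's apparent saving rises by W, but the arm difference does not change: (x − W) − (y − W) = x − y. In a simulation with 25 per arm and assumed W of $0, $5,000 and $10,000, the apparent saving without any true effect was about $0, $5,000 and $10,000. The arm difference stayed at about −$6,000, its assumed true value.

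**3. Where the PCI is counted.** Let C be the PCI cost and D the exercise delivery cost, with other care equal in the two arms. The difference is exercise minus PCI. For illustration C = $10,000, the scale of the added cost of PCI quoted in the Background (not a procedure price), and D = $4,000 (assumed; it does not affect the shift).

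| Treatment of the PCI | Arm difference | Illustration | Shift |
|---|---|---|---|
| Counted once, after the index date | D − C | −$6,000 | none |
| Left out of both windows and of delivery | D | +$4,000 | C |
| Once as delivery and again in the pre-year | D − (C − C) = D | +$4,000 | C |
| In the pre-year only | D − (−C) = D + C | +$14,000 | 2C |
| As delivery and as post-year utilisation | D − 2C | −$16,000 | C, the other way |

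The shift applies in full because every treated PCI patient has the procedure. A single unplanned admission moved from post-year to pre-year is different: it changes one patient's score by twice its cost, but the arm mean by only 2/n of it. That is 8% of the admission's cost at n = 25 and about 6% at n = 32.

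**4. Precision.** Assume equal SDs in the two years and correlation r. Relative to the variance of post-year cost alone, the change score has 2(1 − r) and adjustment for pre-year cost has 1 − r². The SE ratio, change to adjusted, is sqrt(2(1 − r)/(1 − r²)) = sqrt(2/(1 + r)). The detectable difference is for 25 per arm at 80% power (normal approximation): 2.80 × sqrt(2/25) = 0.79 post-year SDs, times the square root of the relative variance.

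| r (assumed) | Variance, change | Variance, adjusted | SE ratio | Detectable, change | Detectable, adjusted |
|---|---|---|---|---|---|
| 0 | 2.00 | 1.00 | 1.41 | 1.12 | 0.79 |
| 0.3 | 1.40 | 0.91 | 1.24 | 0.94 | 0.76 |
| 0.5 | 1.00 | 0.75 | 1.15 | 0.79 | 0.69 |
| 0.65 | 0.70 | 0.58 | 1.10 | 0.66 | 0.60 |
| 0.8 | 0.40 | 0.36 | 1.05 | 0.50 | 0.48 |

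Against unadjusted post-year cost (variance 1.00), the change score is noisier only when r < 0.5. With unequal SDs the threshold is half the ratio of pre-year to post-year SD.

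**The case against.** The strongest reply is that Key Question #3 is a randomised comparison of groups. The work-up happens before randomisation in both arms, so it cannot bias that comparison. This stands. A reader might infer that the trial's cost result would be spurious because of the work-up; step 2 shows that it would not. Only the individual saving is inflated, and the plan sets a comparison with the routine care mean beside it.

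The phrase about individual change scores under Key Question #3 is also ambiguous. In the opening of the Cost Effectiveness Analysis, the same term means changes in perfusion reserve that are linked to costs. This weakens any claim that cost change scores are certainly what is tested. It does not remove the problem, because the net cost itself contains a saving, and the only patient-level construction of that saving is the pre/post one.

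A reader might also infer that the windows open at a different event in each arm, or even that the exercise arm's post-year starts at month 12. The documents do not say so. The date is simply missing, no waiting time for PCI is given, and the second reading does not fit the Timeline: 1.5 years of recruitment plus two years per patient is 3.5 years, against 3 planned. Nor is a comparator lacking. The surrounding text calls PCI routine care, so the non-intervened group is loose wording for the PCI arm.

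Finally, preferring adjustment to subtraction is partly a matter of efficiency. With a common index date both are unbiased under randomisation, and the gain is small if costs in the two years are highly correlated.

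**Conclusion.** The concern holds in a limited form. A patient's own pre/post saving overstates the benefit in both arms, by roughly the cost of the work-up, and should not be reported as the impact of the intervention. The between-arm comparison is not biased by the work-up. It is exposed to an undefined index date and to the missing rule for counting the PCI, which could move the result by one to two times the PCI cost. In the illustration that is enough to reverse its sign. Two definitions of the saving are left unreconciled.

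The precision loss against covariate adjustment is 41% to 5% in standard error for r from 0 to 0.8. It rests on equal SDs, a large-sample formula and an assumed r, since the documents give no cost correlation. The dollar figures rest on assumed costs; the multiples of C do not. The cost findings are called preliminary for a larger study, so this is a change that should be made, not a condition for the trial to proceed.

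**What to change.** - Use the randomisation date as the index date in both arms.
- Define the Key Question #3 outcome as total VA cost in the 12 months from randomisation, delivery plus utilisation, with the PCI and the exercise delivery each counted once. State in which component the index PCI is recorded.
- Compare the arms as randomised, with cost in the 12 months before randomisation as a covariate and not subtracted. The Sample Size Estimates section leaves dropouts out of the analyses; the cost analysis would need an explicit exception, since costs come from VA records.
- Do not present the individual pre-minus-post figure as intervention impact.
- In Healthcare Utilization and Expense Estimates, replace the reference to a non-intervened group with the PCI arm, and use one definition of the saving throughout.

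The cost is SAP wording. The utilisation records for both years are already to be extracted, so no new data source or patient visit is needed. The downside is that an individual patient's saving is no longer reported as an effect.
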